APPENDIX 1.

Adverse event / Adverse drug reaction / Special Situation Reporting Form*

IC4-06593-057-RUS Please send this form immediately by [contact] or by email to [contact] ,					
,		to the associate of	-		
Year of birth or Age	Gender	Height	Weight	Patient's II):
or _	M / F				_ _
Description of adverse ev	ent/reaction/specia	al situation:	Date of ev	vent onset Date of e termination of recove	ion (in case
 □ Death □ Life threatening □ Hospitalization of 	ES (please, specify fr or prolongation of exi hificant disability or i haly/birth defect tant event omitant disease(s)	sting hospitalisation ncapacity (please indicate year	structur Not yet No reco Death Unknow r when first diag	red with consequences (p ral or functional impairme recovered overy vn nosed).	ent)
Causal relationship with i NO D YES f «Yes», please indicate a f «No» or «Not applicable Servier company (which is	□ NOT A lates of the use of in w, please specify w specified in the tab	PPLICABLE nvestigational drug ii whether the adverse e whe below):	vent/special situ	ation is related to the r	
		•	•	mpany:	
List of current medications	Daily dose / route of administration	Dates of int from	ake: to	Indication	
		-			
Name (last, first, patronym Speciality:	ic) of doctor:		Date:	Star	np
Work address: Phone number:(city c	ode)		Signature:	(whenever i	-

*Special situations are cases when adverse event was not observed, but the information should be collected: the impact of the drug during pregnancy/breastfeeding, abuse, misuse, medication error, overdose, off-label use, occupational exposure, or treatment failure...

APPENDIX 2.

The SF-36 health survey questionnaire

(The survey was developed by RAND Health on the basis of Medical Outcomes Study; the Russian version was developed and recommended by the Multinational Center for Quality of Live Research)

Name of patient _____

Date of completion _____

Please circle one number for each statement.

1. In general, would you say your health is?

Excellent	1
Very good	2
Good	3
Fair	4
Poor	5

2. Compared to one year ago, how would you rate your health in general now?

Much better now than one year ago	1
Somewhat better now than one year ago	2
About the same	3
Somewhat worse now than one year ago	4
Much worse now than one year ago	5

3. The following items are about activities you might do during a typical day. Does *your health now limit you* in these activities? If so, how much?

	Yes, limited a lot	Yes, limited a little	No, not limited at all
A. Vigorous activities , such as running, lifting heavy objects, participating in strenuous sports.	1	2	3
B. Moderate activities , such as moving a table, pushing a vacuum cleaner, bowling, or playing golf.	1	2	3
C. Lifting or carrying groceries.	1	2	3
D. Climbing several flights of stairs.	1	2	3
E. Climbing one flight of stairs.	1	2	3
F. Bending, kneeling, or stooping.	1	2	3
G. Walking more than a mile.	1	2	3
H. Walking several blocks.	1	2	3
I. Walking one block .	1	2	3

J. Bathing or dressing yourself.	1	2	3

4. During the *past 4 weeks*, have you had any of the following problems with your work or other regular daily activities as a result of your physical health:

	Yes	No
A. Cut down the amount of time you spent on work or other	1	2
activities.	I	2
B. Accomplished less than you would like.	1	2
C. Were limited in the kind of work or other activities.	1	2
D. Had difficulty performing the work or other activities (for	1	0
example, it took extra effort).	I	Z

5. During the *past 4 weeks*, have you had any of the following problems with your work or other regular daily activities *as a result of any emotional problems* (such as feeling depressed or anxious)?

	Yes	No
A. Cut down the amount of time you spent on work or other	1	2
activities.	I	L
B. Accomplished less than you would like.	1	2
C. Didn't do work or other activities as carefully as usual.	1	2

6. During the *past 4 weeks*, to what extent has your physical health or emotional problems interfered with your normal social activities with family, friends, neighbors, or groups?

Not at all	1
Slightly	2
Moderately	3
Quite a bit	4
Extremely	5

7. How much bodily pain have you had during the past 4 weeks?

None	1
Very mild	2
Mild	3
Moderate	4
Severe	5
Very severe	6

8. During the *past 4 weeks*, how much did *pain* interfere with your normal work (including both work outside the home and housework)?

Not at all	1
A little bit	2
Moderately	3
Quite a bit	4
Extremely	5

9. These questions are about how you feel and how things have been with you *during the past 4 weeks*. For each question, please give the one answer that comes closest to the way you have been feeling. How much of the time during the *past 4 weeks*...

	All of the	Most of	A good	Some of	A little of	None of
	time	the time	bit of the	the time	the time	the time
			time			
A. Did you feel full of pep?	1	2	3	4	5	6
B. Have you been a very	1	2	3	4	5	6
nervous person?						
C. Have you felt so down in the	1	2	3	4	5	6
dumps that nothing could cheer						
you up?						
D. Have you felt calm and	1	2	3	4	5	6
peaceful?						
E. Did you have a lot of energy?	1	2	3	4	5	6
F. Have you felt downhearted	1	2	3	4	5	6
and blue?						
G. Did you feel worn out?	1	2	3	4	5	6
H. Have you been a happy	1	2	3	4	5	6
person?						
I. Did you feel tired?	1	2	3	4	5	6

10. During the *past 4 weeks*, how much of the time has *your physical health or emotional problems* interfered with your social activities (like visiting with friends, relatives, etc.)?

All of the time1	
Most of the time2	
Some of the time	
A little of the time 4	
None of the time5	,

11. How TRUE or FALSE is each of the following statements for you?

	Definitely	Mostly	Don't	Mostly	Definitely
	true	true	know	false	false
A. I seem to get sick a little easier than	1	2	3	4	5
other people					
B. I am as healthy as anybody I know	1	2	3	4	5
C. I expect my health to get worse	1	2	3	4	5
D. My health is excellent	1	2	3	4	5

The survey has the following scales:

- 1. Physical functioning (PF).
- 2. Role physical (RP).
- 3. Bodily pain (BP).
- 4. General health (GH).
- 5. Vitality (VT).
- 6. Social functioning (SF).
- 7. Role emotional (RE).
- 8. Mental health (MH).

All the scales of survey constitute two composite measurements: Physical Component Summary (PCS) (scales 1 to 4) and Mental Component Summary (MCS) (scales 5 to 8).

The method for calculating the main parameters of the SF-36 questionnaire

Scale	Questions	Minimal and maximal values	Possible range of values
1. Physical functioning (PF)	3A, 3B, 3C, 3D, 3E, 3F, 3G, 3H, 3I, and 3J	10 – 30	20
2. Role physical (RP)	4A, 4B, 4C, and 4D	3 – 8	4
3. Bodily pain (BP)	7 and 8	2 – 12	10
4. General health (GH)	1, 11A, 11B, 11C, and 11D	5 – 25	20
5. Vitality (VT)	9A, 9E, 9G, and 9I	4 – 24	20
6. Social functioning (SF)	6 and 10	2 – 10	8
7. Role emotional (RE)	5A, 5B, and 5C.	3 - 6	3
8. Mental health (MH)	9B, 9C, 9D, 9F, 9H.	5 – 30	25

For items 6, 9A, 9E, 9D, 9H, 10, and 11, the count-down is applied.

The formula for calculating the values:

[(actual value of the scale) – (minimal possible value on the scale] : (possible range of values) \Box 100.

Requirements for presenting the results:

- 1. Number of cases per each parameter should be indicated;
- 2. Descriptive statistics: M ± SD, Me (LQ; UQ), % (n/N);
- 3. Accuracy of results (estimates, P value); Confidence interval (for main results of the study) and P value;
- 4. Statistical methods (parametric and non-parametric) and statistical packages should be mentioned.

The recommended statistical packages for the data processing are StatSoft Statistica v.6.0, and SPSS 9.0.

Assessment of patient's compliance with medical therapy [12].

Question	YES	NO
Did you forget to take your medication this morning?		
Since the last visit to the doctor, have you run out of your medication?		
Have you ever taken your medication later than the usual time?		
Have you ever not taken your medication because, on some days, you forgot about it?		
Have you ever not take your medication because you had the impression that it was doing		
more harm than good?		
Do you think that you have too many tablets to take?		

Answer "No" to all the questions: good compliance;

Answer "Yes" to 1-2 questions: minor compliance;

Answer "Yes" to 3 or more questions: noncompliance.

References

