- Percentage (%) of patients at the target levels of the office BP (SBP <140 mm Hg and DBP <90 mm Hg): in general sample and in subgroups (men, women, patients with IHD, diabetes, metabolic syndrome, ISAH, and patients older than 65 years)
- Change in the proportion of patients with different 24-hour BP profiles (dipper, non-dipper, reduced dipper, extreme dipper, nocturnal hypertension)
- Mean change in the 24-hour SBP and DBP (in mm Hg) in patients who performed ABPM
- Mean change in the daytime SBP and DBP (in mm Hg) in patients who performed ABPM
- Mean change in the nighttime SBP and DBP (in mm Hg) in patients who performed ABPM
- Percentage (%) of patients at the target levels of the office BP (24-hour SBP <135 mm Hg and DBP < 85 mm Hg) in patients who performed ABPM
- Change in the mean score of the SF-36 survey (Appendix 2)
- Changes in the treatment compliance score by the Compliance questionnaire (Appendix 3)
- List of SAEs
- List of AEs
- List of AEs that resulted in the withdrawal of the triple FDC of amlodipine / indapamide / perindopril arginine.
- List of ADR
- List of SADR
- List of special situations

Statistical parameters

All parameters will be analyzed using the methods of descriptive statistics. For each parameter, the number of patients, mean, standard error, minimum and maximum values will be indicated.

Statistical analysis

- The baseline characteristics will be analyzed in all the patients who started the treatment (intention-to-treat [ITT] population). In case of significant differences between two treatment groups, the baseline characteristics will be provided for both of them.
- Changes in the SBP and DBP (with the corresponding confidence intervals) will be assessed in the patients who completed the program without major deviations from protocol (per-protocol population [PPP]).
- The analysis of parameters with normal distribution will be performed using the Student's t-test for paired measurements; otherwise the non-parametric Wilcoxon test will be used. The percentage of patients with normalized BP, as well as the percentage of patients who responded to treatment (with 95% confidence intervals), will be calculated.
- Questionnaires: The score for each scale will be calculated as the sum of scores for questions constituting the scale.
- Assessment of the AEs will be carried out in all the patients who started the treatment (ITT population).

Administrative aspects

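### The SF-36 reversal list in Appendix 2 does not fit the printed item codes, so change is mis-scored on bodily pain, general health and social functioning

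*Combined protocol and SAP*

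**What the plan says.** The section on effectiveness and tolerability variables lists "Change in the mean score of the SF-36 survey (Appendix 2". The questionnaire is completed at Visit 1 (week 0) and Visit 4 (week 12). On scoring, the Statistical analysis section says only: "The score for each scale will be calculated as the sum of scores for questions constituting the scale".

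Appendix 2 holds the actual key. It assigns items to eight scales, prints a minimum, a maximum and a range for each, and converts the sum to a 0–100 score. Its reversal rule is: "For items 6, 9A, 9E, 9D, 9H, 10, and 11, the count-down is applied". Item 9 is listed by sub-letter; item 11 is not.

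The answer codes are in the same appendix:

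- Item 1 ("In general, would you say your health is") is coded 1 for excellent to 5 for poor.
- Item 7 ("How much bodily pain have you had during the past 4 weeks") is coded 1 for none to 6 for very severe.
- Item 10 (time that health interfered with social activities) starts at "All of the time1", that is code 1, and ends at code 5 for none of the time.
- Item 11A ("A. I seem to get sick a little easier than" other people) is coded 1 for definitely true to 5 for definitely false.

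The appendix then groups scales 1 to 4 into a physical summary and scales 5 to 8 into a mental summary, without a formula for either.

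**The concern.** A reversal list has one job: to make every item in a scale point the same way. This one omits three items that need reversing (1, 7, 8) and includes three that do not (10, 11A, 11C). No other text in the protocol corrects it or supplies a different key.

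The three affected scales fail in different ways. In social functioning the two items cancel. In general health they partly cancel. Bodily pain is consistent within itself but runs against the correctly keyed scales, including physical functioning, with which it shares the physical summary.

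An analyst who follows the plan would report less pain as a falling score, and an equal improvement on both social functioning items as no change. Both summaries would be built from mis-keyed scales.

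**Working it through.** **Rule applied.** Count-down is read as reversal: reversed score = (highest code + 1) − code. Scale score = (sum − printed minimum) ÷ printed range × 100.

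**The plan's own limits.** Summing the lowest and highest printed codes reproduces six of the eight rows: PF 10–30, GH 5–25, VT 4–24, SF 2–10, RE 3–6 and MH 5–30. Two rows do not reproduce:

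- Bodily pain is printed as 2–12 (range 10). The codes give a maximum of 6 + 5 = 11, so 2–11 (range 9).
- Role physical is printed as 3–8 (range 4). Four items coded 1 or 2 give 4–8.

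**Intended direction.** The text does not say that a higher score is better. The key implies it: PF, VT, RE and MH all come out at 0 for the worst answers and 100 for the best. For example, with 9A and 9E reversed, vitality sums to 4 at worst and 24 at best.

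**Item directions under the printed key**

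| Item | Printed codes | Reversed? | Higher keyed score means |
|---|---|---|---|
| 1 | 1 excellent to 5 poor | no | worse |
| 7 | 1 none to 6 very severe | no | worse |
| 8 | 1 not at all to 5 extremely | no | worse |
| 6 | 1 not at all to 5 extremely | yes | better |
| 10 | 1 all of the time to 5 none of the time | yes | worse |
| 11A, 11C (unfavourable statements) | 1 definitely true to 5 definitely false | yes | worse |
| 11B, 11D (favourable statements) | 1 definitely true to 5 definitely false | yes | better |

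**Social functioning (6, 10; limits 2–10)**

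- Worst health: codes 5 and 1 become 1 + 5 = 6; (6 − 2) ÷ 8 × 100 = 50.
- Best health: codes 1 and 5 become 5 + 1 = 6; again 50.
- In general, write h6 and h10 for the two answers on a 1 (worst) to 5 (best) scale. The printed score is (h6 + 6 − h10 − 2) ÷ 8 × 100 = 50 + 12.5 × (h6 − h10). It depends only on the difference between the two answers.
- It equals 50 in the 5 of 25 answer patterns where they agree. One category better on item 6 alone gives +12.5; on item 10 alone, −12.5. Correct keying gives +12.5 for each.

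**General health (1, 11A–11D; limits 5–25)**

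- All of item 11 reversed. Worst: 5 + 5 + 1 + 5 + 1 = 17; (17 − 5) ÷ 20 × 100 = 60. Best: 1 + 1 + 5 + 1 + 5 = 13; 40.
- Only 11B and 11D reversed. Worst: 5 + 1 + 1 + 1 + 1 = 9; 20. Best: 1 + 5 + 5 + 5 + 5 = 21; 80.
- Of the 16 ways to choose which parts of item 11 are reversed, only 11A with 11C makes all five items agree, and then the scale is inverted. None gives a fully correct scale, because item 1 is never reversed.

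**Bodily pain (7, 8; limits 2–12)**

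- Worst: 6 + 5 = 11; (11 − 2) ÷ 10 × 100 = 90. Best: 1 + 1 = 2; 0.
- Reversing both items but keeping 2–12 gives 0 at worst and (11 − 2) ÷ 10 × 100 = 90 at best, so a pain-free patient cannot reach 100.

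**One category better on every item of the scale**

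| Scale | Printed key | Corrected key |
|---|---|---|
| Bodily pain | −2 ÷ 10 = −20 | +2 ÷ 9 = +22.2 (limits 2–11); +2 ÷ 10 = +20 if 2–12 is kept |
| General health, all of 11 reversed | (2 − 3) ÷ 20 = −5 | 5 ÷ 20 = +25 |
| General health, 11B and 11D only | (4 − 1) ÷ 20 = +15 | +25 |
| Social functioning | (1 − 1) ÷ 8 = 0 | 2 ÷ 8 = +25 |

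**Role physical.** With the printed minimum of 3 it runs from (4 − 3) ÷ 4 = 25 to (8 − 3) ÷ 4 = 125. The 25-point shift is constant and cancels in a change score.

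**The case against.** - **Bodily pain is consistent within itself.** Both items rise with pain, so the score could be read as a pain score on which −20 shows that pain fell. That is fair as far as it goes, and it makes this a different fault from the cancelling items. But the plan never declares such a direction, the correctly keyed scales run from worst to best, and pain enters the physical summary with PF and RP. The inference that it should be reversed is strong, though it remains an inference.
- **The bare 11 may be loose wording for 11B and 11D.** If so, general health points the right way and is only compressed. The −5 is the literal reading, not the only one. Item 1 is still unreversed either way.
- **The one-category changes are illustrations.** The plan gives no expected SF-36 change, so they show direction and scale, not a forecast of bias.
- **The effect on the summaries is unknown.** With no formula printed, neither its size nor its direction can be derived.
- **Some digits are damaged in the extracted text.** The Role physical minimum of 3 may be an artefact or a misprint, and little rests on it. The middle code of item 10 is also lost, but its end codes fix its direction.
- **Standard scoring software would avoid the error.** It would, but the listed variable points to Appendix 2.
- **The SF-36 is neither a primary nor a secondary endpoint.** This stands and limits the weight of the point.

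None of this touches social functioning: items 6 and 10 are coded in opposite directions and both are explicitly reversed.

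**Conclusion.** The key is wrong as written. Change is mis-scored on three of the eight scales. Social functioning is uninformative (50 at both extremes). General health is inverted (60 to 40) or compressed (20 to 80), depending on how 11 is read. Bodily pain is inverted (90 to 0) and has a maximum that the printed codes cannot reach.

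PF, VT, RE and MH are scored correctly, and so is change in Role physical. The primary and secondary endpoints do not use the SF-36.

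The social functioning result needs only the printed codes and the reading of count-down as reversal. The pain result also assumes that higher is meant to be better. The Statistical analysis section mentions only the sum, which leaves the scoring description incomplete but does not contradict the 0–100 conversion. The point should be corrected before the SF-36 is scored.

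**What to change.** In Appendix 2:

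- Reverse items 1, 6, 7, 8, 9A, 9D, 9E, 9H, 11B and 11D. Do not reverse 10, 11A or 11C.
- Set the Role physical minimum to 4.
- Match the bodily pain limits to the codes used: 2–11 (range 9) for the printed codes, or 2–12 (range 10) only if a six-level recode of item 8 is written into the key.

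In the Statistical analysis section, state that the 0–100 scores from Appendix 2 are analysed and that higher means better health.

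Add a programming check that the worst answers give 0 and the best give 100 on every scale. With the corrected list and the 2–11 limits, all eight scales pass; the printed key fails on the three scales above and on Role physical.

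The cost is the reversal list, two table rows and one sentence. Patients circle item-level answers, so any scores already calculated can be redone without new data and with no effect on patients.
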